3.2 Cessation of Glucose-Lowering Medications

At the end of week 10, we will cease all antihyperglycemic medications in participants who achieve a mean 24-hour glucose of <140 mg/dl for at least one week during weeks 8–10. Participants whose baseline 24-hour glucose values are <140 mg/dl must additionally experience a 10% reduction in mean 24-hour glucose to ensure they have genuinely experienced a clinically meaningful improvement. Prior to week 10, participants' medications will not be adjusted unless there are safety concerns or associated adverse events.

3.3 Medication Effect Score

We will quantify the total dosage of antihyperglycemic medications using the MES, which accounts for the potencies and dosages of diabetes medications. The medication score for each individual medication is calculated as: (dose of drug / maximum drug dose) \times a drug-specific adjustment factor,⁶ where the adjustment factor is the expected HbA1c reduction at the maximum drug dose. We will use the adjustment factors determined by Alexopoulos et al.⁷ The

individual scores will be summed to give the MES, which reflects the overall pharmacologic intensity of diabetes treatment.

3.4 OGTTs

At weeks 0, 4, and 12, participants undergo a three-hour OGTT. First, intravenous lines are inserted into participants' antecubital veins. Thereafter, participants consume a 75 g load of glucose. Blood is collected at -5 (fasting), 10, 20, 30, 60, 90, 120, 150, and 180 minutes after glucose ingestion to measure glucose, insulin, and C-peptide levels. The primary OGTT-derived outcome is three-hour mean glucose, which is equivalent to the glucose AUC divided by the duration of the OGTT. Additional outcomes include three-hour mean insulin levels, three-hour mean C-peptide levels, insulin sensitivity, and insulin secretion. Insulin sensitivity and secretion will be estimated using the oral minimal model, a differential equation model that has been validated against the gold-standard hyperinsulinemic-euglycemic clamp method.⁸

3.5 CGM

Participants wear a Dexcom G6® CGM (DexCom Inc.; San Diego, CA) at baseline and throughout the 12-week controlled-feeding intervention. Following the manufacturer's instructions, the sensor is inserted into the subcutaneous abdominal fat and replaced every 7-10 days or as necessary. We will use CGM data to measure mean 24-hour glucose levels, glycemic excursions, and time-in-range metrics. To clean the CGM data, all data collected on the calendar day that a new sensor was inserted will be excluded due to a high mean absolute relative difference (MARD) during the first several hours of sensor usage. Days missing >20% of data will also be excluded from the analysis. Data will be analyzed in one-week segments. Mean 24-

hour glucose levels will be adjusted by the MES using the conversion formula between estimated average glucose (eAG) and HbA1c: 24-hour mean glucose levels + 28.7 × MES. The resultant value, which we call the adjusted mean 24-hour glucose level, represents a person's mean 24-hour glucose levels in the absence of any antihyperglycemic medications. It enables us to fairly compare changes in mean 24-hour glucose when medication dosages change. Finally, glycemic excursions will be quantified using the mean amplitude of glycemic excursions (MAGE),⁹ while time-in-range (TIR) will be quantified using the standard thresholds of 70 (low) and 180 (high) mg/dl, respectively.

3.6 Blood Analyte Assays

Blood analytes include HbA1c, glucose, insulin, C-peptide, and fasting levels of lipids (total cholesterol, LDL cholesterol, HDL cholesterol, and triglycerides). Glucose, total cholesterol, HDL cholesterol, and triglycerides will be measured in serum using a Stanbio Sirrus Clinical Chemistry analyzer (Stanbio Laboratory, L.P.; Boerne, TX). LDL cholesterol will be calculated using the Friedewald equation.¹⁰ Insulin and C-peptide will be measured in serum via immunofluorescence using a Tosoh AIA-II Analyzer (Tosoh Corporation; South San Francisco, CA). HbA1c will be measured in whole blood on a Siemens DCA Vantage Analyzer (Siemens Healthcare Diagnostics; Tarrytown, NY).

3.7 Blood Pressure and Heart Rate

Systolic and diastolic blood pressure are being measured using an automated blood pressure monitor and following the 2019 American Heart Association and American College of Cardiology guidelines.¹¹ After a five-minute rest, blood pressure and heart rate are measured in triplicate, with 1-2 minutes separating each measurement. We will use the average of the second and third measurements.

3.8 Body Weight, Height, and Waist Circumference

Metabolic weight is measured in duplicate to the nearest 0.1 kg on a Scale-Tronix 6702 scale (Hillrom Holdings, Inc.; Chicago, IL) and averaged. Height is measured once to the nearest 0.1 cm at each testing visit using a Heightronic Model 235D stadiometer (QuickMedical; Warwick, RI) and averaged across all measurements. Waist circumference is measured in duplicate to the nearest 0.1 cm at the midpoint between the superior aspect of the iliac crest and the inferior border of the rib cage.

3.9 Magnetic Resonance Imaging and Spectroscopy

At weeks 0, 4, and 12, we measure intrahepatic lipid (i.e., liver fat), pancreatic fat, subcutaneous abdominal adipose tissue (SAAT), and visceral adipose tissue (VAT) using magnetic resonance imaging (MRI) and magnetic resonance spectroscopy (MRS). Participants fast for at least four hours before each scan. All MRI scans are performed at 3 Tesla on a Siemens Prisma whole-body scanner (Siemens Healthcare; Erlangen, Germany). MRS and 3-point M Dixon images are acquired using Siemens LiverLab software. This state-of-the-art technology integrates the multipoint 3D Dixon imaging technique and ¹H MRS for an immediate, comprehensive evaluation of intrahepatic lipid content (%). We will also use the images collected via the 3-point M Dixon method to assess pancreatic lipids. We will assess pancreatic lipid content (%) by identifying three regions of interest free of artifacts and vessels and computing the 3-point M Dixon

The accuracy of the fat fraction metric from this multi-echo fat quantification method has been validated in several fat quantification studies using the following equation:

Fat
$$Fraction_{3-point \ M \ Dixon} = Signal \ Intensity \ (SI)_{FAT} / (SI_{WATER} + SI_{FAT}) \ge 100\%$$
 (1)
We will use trans-axial abdominal images acquired using the LiverLab 3-point Dixon method to
assess visceral adipose tissues and subcutaneous abdominal adipose tissue volume within a 10
cm region of the abdomen between the L1-L5 vertebrae. Images will be analyzed using Slice-O-
Matic software. All analyses will be conducted blinded by [name]

3.10 Sweetness Taste Test

At weeks 0, 4, and 12, we assess preferences for and sensitivity to sweet tastes using a modified version of the sweetness taste test described by Asao et al.¹² Participants undergo the test after completing each OGTT but before consuming any subsequent food or beverage. Eight logarithmically spaced quantities of sucrose ranging from 0.053 g to 6.846 g are dissolved in 10 ml distilled water to produce sucrose concentrations ranging from 0.015 M to 2.000 M. Approximately 5 ml of each solution is randomly assigned to a cup numbered 1 through 8, and this is repeated a second time in an identically sequenced set of eight cups. This randomized sequence for this study was determined before the study started and is identical for all participants and across all time points. Participants take a sip of the sucrose solution in each cup, swish it around in their mouths for five seconds, and expectorate the solution. Participants indicate (a) how much they liked the sucrose solution (the pleasantness) and (b) how sweet they thought it was (the intensity) on a 100-point visual analog scale. Participants then rinse their mouths with plain water before continuing this process for the remaining sucrose solutions, with

the interval between tastings being 30-60 seconds. After a three-minute break, the participants repeat the process with the second set of cups.

3.11 Questionnaires

We are assessing diet satisfaction, appetite, food cravings, eating behaviors, mood, quality of life, and depression using questionnaires. At weeks 0, 4, and 12, participants complete the following questionnaires:

- Profile and Mood States-Short Form (POMS-SF): assesses current mood states and total mood disturbances;¹³
- Patient Health Questionnaire-9 (PHQ-9): measures the severity of depression;¹⁴
- CDC's Health-Related Qualify of Life (HRQoL): measures quality of life;¹⁵
- Food Craving Inventory II (FCI-II): measures food cravings for various categories of food;¹⁶
- The fruit subsection and fruit juice questions of the Diet History Questionnaire (DHQ): assesses fruit consumption via a semi-quantitative food frequency questionnaire.¹⁷
 Using the same question format as in the DHQ, we also ask participants how often and how much they eat different subcategories of fruit (i.e., raw, frozen, dried, cooked, and juice);
- The fruit and vegetable questions of the 2007 Food Attitudes and Behaviors (FAB) survey: measures attitudes and behaviors related to fruit and vegetable consumption.¹⁸ We are using most of question 2 (except for Q2A, Q2C, Q2H, Q2I, Q2K, Q2L, Q2P, Q2Q, Q2S, Q2T, Q2V, Q2AA, Q2CC, Q2EE) and questions 3, 4, 5, 6, 7, and 9 from

section 1; questions 24, 29, 30, 31, and 32 from section 4; all questions from section 6 except for Q43; and all questions in section 7;

- Fruit Liking Visual Analog Scales (VAS): a 100-mm VAS custom-designed for this study to assess how much participants like subcategories of fruit (i.e., fresh, frozen, fruit smoothies, dried, cooked, canned, and fruit juice);
- Diet Satisfaction Questionnaire: a series of VAS questions to assess both appetite and diet satisfaction. Specifically, we ask about overall diet satisfaction, food tastiness, energy levels, hunger, fullness, stomach fullness, desire to eat, capacity to eat, cravings, and feelings of deprivation. Appetite-related questions are retrospectively assessed over the past week.

3.12 Food Records

Participants complete three-day food records at baseline. Participants complete the records on two weekdays and one weekend day. The records will be analyzed using the Nutrient Data System for Research (NDS-R; University of Minnesota, Minneapolis, MN; version 2014). Dietary endpoints will include energy intake, macronutrient composition, % of calories (or servings/day) of food groups, and the Healthy Eating Index (HEI).¹⁹ We will also test whether baseline HEI predicts changes in glycemic control.

We initially instructed participants to complete baseline food records during baseline CGM data collection and weeks 4 and 12. However, after examining CGM data from the first three completers, we discovered that participants drastically altered their eating patterns and ate substantially less and/or healthier on days that they filled out the food records. To eliminate these data validity issues moving forward, we subsequently amended the protocol to have participants

complete the baseline food records before the second screening visit (i.e., before baseline CGM data is collected) and to eliminate the records at weeks 4 and 12. For the first three completers, since some of their baseline CGM data is invalid, we will use the mean response from the remaining completers to extrapolate which days of CGM data are valid.

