1.7 Screening

Interested individuals are prescreened via an online questionnaire and/or by phone, and those who pass prescreening are invited to screen in person. At the first screening visit, applicants sign the consent form, are screened against the eligibility criteria, and have their blood drawn to run a metabolic panel and measure HbA1c. After the first screening visit, the study physician reviews each applicant's laboratory results and medical history. Applicants deemed medically eligible then complete a three-day food record before returning for a second screening visit. During the second screening visit, we conduct a 30-45 minute semi-structured interview called a Barriers Interview. During the Barriers Interview, we ensure that each participant understands the demands of the study, and we assess any psychological, behavioral, and logistical barriers that may impede study participation. Only applicants capable of meeting all study demands are enrolled.

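### Food-record reactivity is repaired only in the first three completers' baseline CGM; their week-4 record days are left in, which can bias the secondary week 0–4 CGM contrast towards improvement

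*Combined protocol and SAP*

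**What the plan says.** Section 3.12 describes the first schedule: "We initially instructed participants to complete baseline food records during baseline CGM data collection and weeks 4 and 12". After looking at CGM data from the first three completers, the study team found that "participants drastically altered their eating patterns and ate substantially less and/or healthier on days that they filled out the food records". That statement is not limited to baseline.

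For later participants, the baseline record was moved ahead of baseline CGM, and the amendment was also "to eliminate the records at weeks 4 and 12". Section 5 gives the same reason for dropping those two records.

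For data already collected, the text reads "For the first three completers, since some of their baseline CGM data is invalid", and the remedy is that "we will use the mean response from the remaining completers to extrapolate which days of CGM data are valid". Weeks 4 and 12 are not mentioned.

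Section 3.5 has CGM worn at baseline and throughout the intervention, and says "Data will be analyzed in one-week segments". It excludes sensor-insertion days and days with more than 20% of data missing. It does not exclude record days.

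**The concern.** The plan treats week-4 and week-12 records as a threat to validity for future participants, but gives no rule for the same records where they had already been scheduled. Followed as written, it cleans week 0 for the three early completers and leaves their later record days in.

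Cleaning baseline is right in itself. The difficulty arises only where reactivity also occurred later and is left in. Glucose at that later time point is then too low against a cleaned baseline, and part of the apparent fall comes from record-keeping and not from the diet.

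Week 4 is where this can happen. Under section 2.2, fruit supplies 50% of week-4 calories and the rest is the participant's own reduced habitual diet, so a record can still change what is eaten. The week 0–4 and week 4–12 comparisons are both pre-specified as secondary in section 4.4, and section 2.2 presents the ramp-up as preliminary evidence on whole fruit alone. The first contrast would be biased towards improvement. The second would be biased towards worsening if week 4 is lowered more than week 12.

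**Working it through.** The plan states no figure on this point, so there is none to reproduce. The possible size is worked out below.

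**Inputs from the documents**
- Record days per time point: 3, being two weekdays and one weekend day (section 3.12).
- CGM segment: one week, so 7 days, or 6 if a sensor-insertion day is dropped (section 3.5).
- Participants named in the repair: 3. Planned completers: 16 (sections 3.12 and 4.3).

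**Assumptions**
- X, the fall in mean glucose on a record day: 10–30 mg/dl.
- f, the share of baseline reactivity that persists at the later time point: 1, 0.5 or 0.1.
- All three record days fall inside the analysed week.

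**Formulas**
- Shift in one participant's weekly mean = f × X × 3 / (usable days).
- Shift in the group mean = that value × 3/16.

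**Individual shift at f = 1**
- 7 days: 10 × 3/7 = 4.3 to 30 × 3/7 = 12.9 mg/dl.
- 6 days: 10 × 3/6 = 5.0 to 30 × 3/6 = 15.0 mg/dl.

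**Group shift at f = 1**
- Smallest: 4.29 × 3/16 = 0.80 mg/dl.
- Largest: 15.0 × 3/16 = 2.81 mg/dl.

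| Share persisting (f) | Individual weekly mean too low by (mg/dl) | Mean of 16 too low by (mg/dl) |
|---|---|---|
| 1 (upper limit) | 4.3–15.0 | 0.8–2.8 |
| 0.5 | 2.1–7.5 | 0.4–1.4 |
| 0.1 | 0.4–1.5 | 0.08–0.28 |
| 0 | 0 | 0 |

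**Which row fits which week.** At week 4 about half of intake is self-chosen, so f = 1 is a ceiling and f = 0.5 a reasonable middle value. At week 12 food is provided and eating is video-recorded, with two break meals a week as the exception (sections 2.3 and 2.7), so f between 0 and 0.1 is the illustrative range.

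**Effect on a test.** Assume an SD of change of 20–30 mg/dl and no true effect. The standard error of the mean change is SD/√16, or 5–7.5 mg/dl. Treating the group shift as a non-centrality of shift/SE, with 15 degrees of freedom, a two-sided 5% paired t-test rejects in:
- 5.1–8.2% of trials at f = 1;
- 5.0–5.8% at f = 0.5;
- 5.00–5.03% at f = 0.1.

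The 8.2% needs the largest X, the smaller SD, 6 usable days and full persistence together.

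**Carry-over through a linear time effect.** Section 4.4 allows time to be linear. With visits at 0, 4 and 12 weeks and complete data, mean time is 16/3 and the sum of squared deviations is 28.44 + 1.78 + 44.44 = 74.67. Week 4 then enters the fitted 12-week change with weight 12 × (4 − 5.33)/74.67 = −0.21. A week-4 mean that is 0.8–2.8 mg/dl too low moves that change by 0.2–0.6 mg/dl, towards worsening.

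**After the fix.** If record days are excluded at all three time points, the shift is 0 whatever X and f are.

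**The case against.** The strongest reply is that the result which matters most is hardly exposed. The primary comparison is week 0 against week 12. At week 12 participants eat provided food on video, and compliance below 80% is grounds for withdrawal. A food record has little room to change intake there, so removing reactive baseline days is a correction and not a bias. This stands. A reader might infer that the primary contrast is biased towards improvement, or that the week-12 classification against 140 mg/dl is distorted for these three. The documents do not support either inference. The medication-cessation decision also rests on CGM from weeks 8–10, when no food record was scheduled.

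Further points stand in part:
- The week 0–4 contrast is secondary, and mean 24-hour CGM glucose is fourth in the outcome hierarchy. That limits the consequence but does not remove the bias from a contrast the plan says it will report.
- The paired t-test is only a gauge. Section 4.4 plans mixed models or splines. A linear time effect does dilute a distorted week 4, but then passes a small part of it into the 12-week estimate.
- It is inferred from the instruction that the three kept the later records. The text also does not say outright that low days are deleted, and its phrase about valid CGM days could be read more widely than baseline. That ambiguity itself needs resolving.

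Two other inferences should not be drawn. Participants enrolled before the amendment but not yet finished may exist, but the documents report none. Table S2 marks the food record under baseline, which might suggest that it still overlaps CGM. The table has no screening column, however, and section 1.7 has applicants "complete a three-day food record before returning for a second screening visit", so the mark is not evidence of overlap.

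**Conclusion.** The concern holds for week 4. As written, the plan repairs baseline and leaves week 4 unrepaired for three of 16 completers, although it accepts that the later records raised the same validity problem. If those participants kept their week-4 records, the week 0–4 CGM contrast is biased towards improvement, by at most 0.8–2.8 mg/dl in the group mean and about 0.4–1.4 mg/dl if half the reactivity persists. The week 4–12 contrast is biased towards worsening if week 4 is lowered more than week 12. The individual shift, at most 4–15 mg/dl, also bears on the CGM trajectory analysis in section 4.4.

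For the primary week 0–12 contrast, a shift of about 0–0.3 mg/dl is the reasonable expectation from week-12 record days, and for the week-12 threshold outcome an individual shift of 1.5 mg/dl or less.

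All sizes rest on the assumed 10–30 mg/dl, on the assumed persistence, and on the record days falling in the analysed week. The direction at week 4 does not depend on the size assumed, provided that eating less or more healthily lowers glucose.

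**What to change.** In section 3.12, with a cross-reference in the cleaning rules of section 3.5, state one rule: for every participant who kept food records while wearing CGM, the recorded calendar days are excluded from the CGM segments at weeks 0, 4 and 12. The rule depends on dates and not on glucose values, and it applies to anyone who meets the condition, whatever the order of completion. At baseline it would take the place of inferring valid days from other participants. The study team linked eating patterns to record days, so the dates should be available.

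Add a sensitivity analysis that keeps the week-12 record days, since those are probably sound controlled-feeding data.

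The cost is a sentence or two and no new data. The downside is precision: the affected participants would have 7 − 3 = 4, or 6 − 3 = 3, valid CGM days in those weeks.

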1.3 Primary and Secondary Outcomes

The primary outcome is glycemic control. Glycemic control is difficult to accurately assess whenever antihyperglycemic medications doses change, as changing doses can mask improvements in standard glycemic outcomes. Therefore, we define an individual has having an improvement in glycemic control if s/he needs a lower dose of antihyperglycemic medications (if medication doses change) or has lower mean glucose levels (if medication doses do not change). We will use the following hierarchy of glycemic outcomes:

- 1. Achieving non-diabetic glycemia without antihyperglycemic medications (assessed as a binary outcome and analogous to T2D remission without the 3-month requirement);
- Total dosage of antihyperglycemic medications, as measured by the medication effect score (MES);
- 3. Mean glucose during a three-hour OGTT; and
- 4. Mean 24-hour glucose as measured by continuous glucose monitoring (CGM), adjusted for any changes in medication doses via the MES (see Section 4.5).

We decided to use mean 24-hour glucose as measured by CGM in lieu of HbA1c because CGM more accurately assesses the present glycemic status over the previous week, whereas HbA1c is a lagging indicator of glycemic control. The hierarchy implies that a positive or negative outcome in an upper level will always supersede any findings from lower levels in the hierarchy. In particular, if glucose-lowering medication dosages change, then assessments 1 and

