2 will supersede assessments 3 and 4 since changes in glucose-lowering medications confound the interpretation of glycemic data. If there are no changes in glucose-lowering medications, then we will use assessments 3 and 4 to determine whether there are changes in glycemic control. We will interpret the data from assessments 3 and 4 as follows. We will interpret assessment 3 (OGTT) to indicate whether the intervention improves or exacerbates glucose intolerance and underlying defects in glucose metabolism. If there is no change in assessments 1-3, we will interpret assessment 4 (CGM) to reflect only acute changes in the glycemic load and macronutrient composition of the diet. For instance, the intervention may increase mean 24-hour glucose levels in a participant who eats a low-carbohydrate diet at baseline, but this increase may simply reflect switching to a higher carbohydrate diet, not a worsening of glucose metabolism.¹ As another example, the intervention may decrease mean 24-hour glucose levels in a participant who eats a higher glycemic load diet at baseline, but this decrease may reflect switching to a lower glycemic load diet, not an improvement in glucose metabolism per se.

The secondary outcomes are liver fat, pancreatic fat, cardiovascular risk factors, and ancillary measures of glucose metabolism:

- Liver fat, as measured by magnetic resonance imaging and spectroscopy (MRI/S);
- Pancreatic fat, as measured by MRI/S;
- Insulin secretion, as measured by the oral minimal model;
- Insulin sensitivity, as measured by the oral minimal model;
- Mean insulin and C-peptide levels during the OGTT;
- Time-in-range metrics from CGM;
- Mean amplitude of glycemic excursions from CGM;
- HbA1c;

- Fasting glucose;
- Blood pressure;
- Heart rate; and
- Lipids (total cholesterol, LDL cholesterol, HDL cholesterol, and triglycerides).

Additional outcomes include body composition (subcutaneous abdominal fat, visceral fat, and waist circumference), preferences for and sensitivity to sweet tastes, diet satisfaction, food cravings, eating behaviors, mood, quality of life, and depression.

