2.2 Ramp-Up Phase: Weeks 1–4

We give participants a four-week ramp-up period to acclimate to the high fiber and low energy density of the diet. The ramp-up period allows participants to adapt to eating low-energy-density food and overcome any transient gastrointestinal or bowel symptoms. The ramp-up period also provides preliminary data on the effects of whole fruit alone on cardiometabolic health before the remainder of participants' diet becomes a Mediterranean diet. During the ramp-up period, participants gradually eat more whole fruit as follows:

- Days 1-2: 10% of calories in the form of a frozen fruit smoothie;
- Days 3-7: 20% of calories in the form of a frozen fruit smoothie;
- Week 2: 30% of calories, with 25% as a smoothie and 5% as dried fruit;
- Week 3: 40% of calories, with 25% as a smoothie, 10% as dried fruit, and 5% as a fresh-fruit salad;

• Week 4: 50% of calories, with 25% as a smoothie, 12.5% as dried fruit, and 12.5% as a fresh-fruit salad.

To remain weight stable, participants are instructed to reduce their habitual diet in proportion to the amount of fruit added.

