4.2 Blinding

By necessity, participants and intervention staff are unblinded. Nursing staff unaffiliated with the study assess blood pressure and heart rate and perform the OGTTs blinded. Laboratory

technicians unaffiliated with the trial conduct the biochemical assays. MRI image analysis will be performed blinded. Data will be cleaned blinded by aggregating all time points together and/or by scrambling the order of timepoints.

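### Baseline CGM days for the first three completers are to be chosen by an undefined response of the other completers, although the plan itself ties the distortion to dated food-record days

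*Combined protocol and SAP*

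**What the plan says.** Section 3.12 describes the original schedule: "We initially instructed participants to complete baseline food records during baseline CGM data collection and weeks 4 and 12". It then reports, "after examining CGM data from the first three completers", that "participants drastically altered their eating patterns and ate substantially less and/or healthier on days that they filled out the food records". The baseline record was moved to before CGM collection, and the week-4 and week-12 records were dropped. For the three people already through the study, the section calls some of their baseline CGM data invalid and continues: "we will use the mean response from the remaining completers to extrapolate which days of CGM data are valid".

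Nothing else in the document defines that rule:
- Section 3.5 excludes only sensor-insertion days and days with more than 20% of data missing.
- Sections 4.4 and 5 give no day-selection rule and no analysis without the three.
- Section 4.2 says data are cleaned blinded, by pooling time points and/or "by scrambling the order of timepoints".

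Section 1.3 makes CGM mean 24-hour glucose the fourth level of the primary hierarchy, in which "a positive or negative outcome in an upper level will always supersede any findings from lower levels in the hierarchy".

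**The concern.** The rule names no variable, time window, distance, cut-off or minimum number of days. Whether the response meant is the others' change on the diet or their glucose pattern, values of the outcome variable in other people select the data kept for these three. The choice is still open after the three participants' own CGM data have been looked at. Under the amended schedule the remaining completers kept no record during CGM, so their data cannot show which days a record distorted.

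The results at stake are those measured from baseline CGM: mean 24-hour glucose, time in range, MAGE, the trajectory analysis, and the percentages improved or worsened where CGM decides. If days are chosen because they agree with the group's change, these three will look like the group by construction and the standard error will be too small.

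**Working it through.** **The plan's own figure.** Section 4.3 gives 80% power at d = 0.78 for 16 completers (two-sided paired t-test, 5%). Exact power uses the noncentral t with n − 1 degrees of freedom and noncentrality d√n:
- n = 16: 0.78 × √16 = 3.12, power 83.0%.
- n = 15: power 80.2%.
- n = 13: 0.78 × √13 = 2.81, power 73.3%.

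The plan's figure is slightly conservative and is not disputed.

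**Inputs from the documents.** 16 completers, 3 affected (3/16 = 18.75%); 3 record days per person (Section 3.12); week 0 vs 12 as the primary comparison, two-sided 5% (Section 4.4).

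**Inputs assumed.** 6 usable baseline days, 3 of them record days; 6 week-12 days; daily SD 10, 15 or 25 mg/dl; between-person SD of change 8, 12 or 20; record-day shift 0, −15 or −30 mg/dl; true mean change 0; 20,000 simulated trials per combination. Each person's change is the week-12 mean minus the mean of the baseline days kept, tested with a one-sample t on the changes.

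**Rejection rate at nominal 5%, distortion confined to record days:**

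| Handling of the three | Rejection rate |
|---|---|
| Subset of at least 3 days that best fits the others' mean change | 6.2–8.9% |
| Drop days more than 2 SD from the person's own baseline median (SD from the other 13), no shift | 4.8–5.2% |
| Same rule, with a shift | 5.4–10.0% |
| Keep all days, with a shift | 5.4–10.9% |
| Drop record days | 4.7–5.2% |
| Exclude the three | 4.7–5.2% |

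Under the best-fit reading the SD of change is 0.881–0.953 times that under dropping record days, that is, 5–12% smaller.

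**A different set-up.** With 7 baseline days, the 4 closest to the others' change kept, SD of true change 15, daily SD 10–20 and a shift of 0 or −20, the rates are 6.5–7.9% for matching and 4.8–5.1% for dropping record days.

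**Limiting case (not the stated rule).** Suppose the three changes equal the mean of the other 13. The sum of squares is then 12s² on 15 degrees of freedom, so the variance is 0.8s². The ratio of computed to true standard error is √(0.8/16) / √(1/13) = 0.806. The test rejects when |t₁₂| > 2.131 × 0.806 = 1.718, which has probability 11.1%.

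**Spill-over onto non-record days.** If the other baseline days carry half of a −30 shift, dropping record days leaves a bias of 3/16 × 15 = 2.8 mg/dl toward a glucose rise. It then rejects about 6.4–11%, against about 8.1–11.2% for best-fit matching. At a quarter of −30 the bias is 3/16 × 7.5 = 1.4 mg/dl and dropping record days rejects 5.3–7.4%. Excluding the three stays at 4.7–5.4% throughout.

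**Precision of a short baseline.** The standard error is daily SD/√days. Three days give 10/√3 = 5.8 to 25/√3 = 14.4 mg/dl; two days give 7.1 to 17.7 mg/dl.

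**The case against.** - **The size depends on a reading the plan does not state.** This stands. Matching on change is one interpretation; under the non-matching rule with no shift there is no inflation. All glucose inputs are assumed, and the planned mixed or spline models may behave differently from a t-test.
- **The date rule may not suffice.** This stands. Section 3.12 does not say that the other baseline days are clean, and with heavy spill-over the advantage of the date rule can nearly vanish. That is the reason for also reporting results without the three.
- **The date rule is not wholly free of outcome data.** This also stands. Record days were identified as a problem by looking at these participants' CGM. Only the application of the rule is outcome-free.
- **Little hangs on level 4.** This is largely right. The trial is a pilot not sized on power, upper levels take precedence, and if levels 1–3 show no change "we will interpret assessment 4 (CGM) to reflect only acute changes in the glycemic load" and macronutrient composition of the diet. It limits the weight of the point but does not justify the rule.

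A reader might also infer that week-12 record days bias the primary comparison toward benefit. The documents give little support for that: from week 5 participants eat only provided food apart from two break meals a week (Section 2.3), on video, with compliance below 80% grounds for withdrawal (Section 2.7). Week 4 differs, because half of intake was still self-chosen: "participants are instructed to reduce their habitual diet in proportion to the amount of fruit added".

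A conflict with the blinded cleaning in Section 4.2 is likewise not demonstrated. It arises only if that section covers CGM and days are picked by agreement with a change from baseline.

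**Conclusion.** The point holds as a flaw of method with limited reach. For 3 of 16 participants an undefined rule lets other people's outcome data choose baseline CGM days, when a date criterion follows from the plan's own diagnosis. If the rule means matching on change, the pull toward the group needs no particular inputs. Its size does: about 6–9% rejection at nominal 5% and an SD of change 5–12% too small, under the assumptions listed and with no spill-over. A reader should not conclude that the planned analysis is known to be inflated by this amount.

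The impact is mainly on level 4 and the CGM-derived secondary outcomes. It would be too strong to say that nothing above level 4 can be affected: Section 3.2 uses baseline 24-hour glucose in its 10% reduction test, which feeds levels 1 and 2. For three people who had already completed, that decision probably predates the rule, but the plan does not say which baseline value was used. The change is worth making before CGM outcomes are analysed.

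**What to change.** Replace the sentence in Section 3.12 with the following, before CGM outcomes are analysed:

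1. For the first three completers, exclude the baseline calendar days on which a food record was kept (assuming the dates are on file), in addition to the Section 3.5 exclusions. Use no glucose value to pick days.
2. Fix in advance a minimum number of remaining baseline days, below which baseline CGM is set to missing. The number is the team's choice; the standard errors above show what two or three days buy.
3. Report all baseline-referenced CGM results without these three as an ordinary sensitivity analysis, because the date rule cannot remove spill-over. Do not require both analyses to fall below 5%: that would halve the false-positive rate to 2.5–2.9% and cut simulated power to 70–71%.
4. State whether the date rule also applies to any week-4 record days. No exclusion is needed at week 12 beyond an optional check.
5. State which baseline 24-hour glucose value was used for these three in the Section 3.2 test.

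The cost is a few sentences and one extra analysis, with no new data. The downsides are a noisier or missing CGM baseline in up to three people, possibly weighted to weekdays, and lower power in the 13-person analysis (73.3% against 83.0% at d = 0.78).
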